## **H00014860 Acetazolamide on High-Altitude Pulmonary Edema**

**Version 2 – 02/10/2018**

### **INVESTIGATOR STUDY PLAN**

Ultrasound images will be stored on password-protected encrypted Android tablets that are used to gather ultrasound images. There is limited internet connectivity in this remote region of Nepal and upload of ultrasound images is not always feasible in the field.

No medical record review will be done.

No use of a Humanitarian Use Device will be employed.

#### **12. DATA AND SPECIMEN BANKING\***

N/A

#### **13. Data Analysis and Management\***

Previous studies in lung ultrasonography suggest that a minimum of 14 subjects will be needed to provide 80% power to detect a statistically significant difference in ultrasound lung comets. Between 20-30 total subjects are expected.

For data analysis, Fisher's exact test will be used to compare categorical variables. Continuous variables will be analyzed with paired Student's t-test. Linear regression models will be used to assess correlations between ultrasound lung comets and vital signs. In all cases p values < 0.05 will be considered significant. Data will be reported as mean +/- SD

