**4. OBJECTIVES\***

The overall goal of this study is to detect preclinical signs of HAPE by lung ultrasonography and evaluate the effectiveness of acetazolamide at decreasing pulmonary edema by using ultrasound.

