**10. STUDY ENDPOINTS\***

Primary outcome measures: 1.) Pulmonary edema detected in lung ultrasound exams before and after taking acetazolamide.

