### 11. PROCEDURES INVOLVED\*

After informed consent has been obtained, subjects will be randomized to receive either of the study medications medication: 250mg of acetazolamide or a placebo pill. Investigator will be blinded as to which arm of the study the patient is enrolled. Medications will be obtained from the UMass Pharmacy in individual blister packs. We will ensure that acetazolamide and the chosen placebo pill look similar. Any identifying information on the blister pack will be obscured by a black marking pen, if necessary. Medications will then be inserted into small opaque envelopes and marked with only a number. Numbers will be assigned to medications by use of the random number generator function (=RANDBETWEEN(1,30\*)) (\*The final number will depend on the total number of subjects) in Excel with the top half of the list being assigned Acetazolamide and the bottom half placebo pill. The list will then be sorted in numerical order in Excel. When a subject enrolls, a number will be assigned in order. Blinding of the numbers and assigned medications as well as the assembly of the envelopes will be done prior to leaving UMass by PI's faculty advisor who will not be involved in medication administration.

At each of the time points noted in #9, lung ultrasound exams will be done at bedside in a private location to measure the total ultrasound lung comets (an ultrasound finding for pulmonary edema) for a "comet score." One (1) single dose of 250mg acetazolamide or placebo will be given at Everest Base Camp (Data Collection #4) and a comet score will be measured again 12 hours after acetazolamide or placebo is given. Previous studies have shown that comet scores increase with altitude and given that Everest Base Camp is the highest altitude the subjects will be residing at, it is believed that we will find the biggest decrease in comet score if acetazolamide is given at this point. The subject's heart rate and oxygen saturation will also be collected via a pulse oximeter.

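### The trial randomises to acetazolamide or placebo, but the plan names no between-arm test of the comet score, and its figure of 14 subjects should not be read as the power of the drug comparison

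*Combined protocol and SAP*

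**What the plan says.** Section 4 (Objectives) sets two goals: to "detect preclinical signs of HAPE by lung ultrasonography and evaluate the effectiveness of acetazolamide at decreasing pulmonary edema by using ultrasound".

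Section 11 (Procedures Involved) describes a blinded, placebo-controlled allocation from a numbered list, "with the top half of the list being assigned Acetazolamide and the bottom half placebo pill". One dose is given at Everest Base Camp (Data Collection 4), and "a comet score will be measured again 12 hours after acetazolamide or placebo is given". Both arms therefore have a pre-dose and a post-dose score.

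Section 10 (Study Endpoints) gives the primary outcome as "Pulmonary edema detected in lung ultrasound exams before and after taking acetazolamide". Placebo is not mentioned.

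Section 13 (Data Analysis and Management) says that earlier studies suggest "a minimum of 14 subjects will be needed to provide 80% power to detect a statistically significant difference in ultrasound lung comets", and adds: "Between 20-30 total subjects are expected". It names three methods:
- Fisher's exact test, for categorical variables.
- For the rest: "Continuous variables will be analyzed with paired Student's t-test".
- Linear regression, for comets against vital signs.

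None of these is assigned to acetazolamide versus placebo on the comet score.

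**The concern.** The placebo arm exists to show what happens to comet scores over the 12 hours without the drug. A paired test of before against after makes no use of it. A fall common to both arms could be reported as a drug effect, and a common rise could hide a real benefit. Section 11 says that "Previous studies have shown that comet scores increase with altitude", but the documents do not say how scores move during a further 12 hours at Base Camp, so neither direction can be excluded.

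The second part concerns how the sample size will be read. Someone who sees 14 needed and 20 to 30 expected may conclude that the drug question is comfortably powered. Nothing in section 13 links the 14 to that question. If the drug result is then non-significant, it may be taken as evidence of no effect when the interval still allows sizeable ones.

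**Working it through.** **Inputs.** From section 13: 14 subjects, 80% power, a significance level of 0.05, and 20 to 30 subjects expected. From section 11: equal allocation, hence 10 to 15 per arm. Not given: effect size, SD, sidedness, contrast, and whether 14 counts pairs, subjects per arm or a total. I assume two-sided 5%. Effects are in SDs of the within-subject change. Power is from the noncentral t distribution.

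**1. Can the 14 be reproduced?** Not forwards, because there is no effect size or SD. Solving backwards for 80% power gives:

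| Reading of 14 | Degrees of freedom | Noncentrality | Implied effect d |
|---|---|---|---|
| 14 pairs | 13 | d × √14 | 0.81 SD |
| 14 per arm, two arms | 26 | d × √(14/2) | 1.10 SD |
| 14 in total (7 + 7) | 12 | d × √(7/2) | 1.63 SD |

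Each reading is possible. If 14 counts pairs, what 20 to 30 subjects provide at 0.81 SD depends on who supplies the pairs:
- Altitude contrast, every subject a pair (20 to 30 pairs): 93% to 99% power.
- Before against after in the acetazolamide arm only (10 to 15 pairs): 63% to 83% power.

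The figure can be neither confirmed nor refuted from these documents.

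**2. What the paired test does with a common shift.** Suppose both arms shift by s SD over the 12 hours and the drug does nothing. The paired test in the acetazolamide arm has noncentrality s × √n and n − 1 degrees of freedom. The values of s are assumptions.

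| Assumed s | n = 10: noncentrality, P(significant) | n = 15: noncentrality, P(significant) |
|---|---|---|
| 0.25 | 0.25 × √10 = 0.79, 11% | 0.25 × √15 = 0.97, 15% |
| 0.50 | 0.50 × √10 = 1.58, 29% | 0.50 × √15 = 1.94, 44% |

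The nominal rate is 5%. A between-arm test of the change keeps that rate, because the common shift cancels.

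**3. What the between-arm comparison can show.** For a two-sample t-test of the change with n per arm, noncentrality is d × √(n/2) with 2n − 2 degrees of freedom. Solving for 80% power:
- n = 10: d = 1.32 SD.
- n = 15: d = 1.06 SD.

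The 95% CI half-width is t(0.975; 2n − 2) × √(2/n):
- n = 10: 2.101 × √0.2 = 0.94 SD.
- n = 15: 2.048 × √0.1333 = 0.75 SD.

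No loss rate is stated. With an assumed 10% to 20% loss, 20 enrolled become 18 or 16 evaluable (1.41 or 1.51 SD), and 30 become 27 or 24 (1.12 or 1.20 SD).

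**4. Effect of adjusting for the pre-dose score.** If pre-dose and post-dose scores have equal variance σ² and correlation r, the change has variance 2σ²(1 − r) and the regression residual has variance σ²(1 − r²). The ratio is (1 + r)/2, so the figures in step 3 shrink by about √((1 + r)/2): 0.87 at an assumed r = 0.5 and 0.97 at r = 0.9, ignoring the one lost degree of freedom.

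**The case against.** **The endpoint and the test agree with each other.** Section 10 is a before-and-after outcome and a paired t-test suits it. That stands as a description, but it means the mismatch lies with the randomised design and the section 4 goal of evaluating effectiveness. It also means that section 10 needs changing as well as section 13.

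**Fisher's exact test could compare the arms.** It could if edema were scored yes or no. No cut-off is defined, and section 11 specifies a comet score, so this is not a usable primary comparison as it stands.

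**The basis for 14 may be elsewhere.** Sections 5 and 11 refer to an attached grant proposal for background and scanning methods. It is not among the documents and may hold the calculation. The point is therefore limited to what these documents say. A basis held there would still leave section 13 without a between-arm test.

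**The false-positive rates are hypothetical.** The shifts have no source, and the rates assume that the acetazolamide arm is tested alone. Section 13 does not forbid looking at the placebo arm as well. They illustrate the mechanism and do not forecast its size.

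**Enrolment is fixed by the trek.** Sections 24 and 25 tie the number to trip registration. This is accepted, and no increase is sought.

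**A reader might infer that the 14 is wrong or that the drug comparison is underpowered.** The documents support neither. Carrying 0.81 SD over to the between-arm contrast would give only 40% to 57% power with 10 to 15 per arm. But that takes an effect in SDs of one change and applies it to a different contrast whose SD is unknown. Nor can 1.1 to 1.3 SD be called implausibly large without an SD for the 12-hour change.

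**Conclusion.** The concern holds as a gap in the analysis, with a secondary gap in the sample size statement. The plan pays for a randomised placebo control and then names no test of the comet score that uses it. This should be settled before data are seen, because the choice between a within-arm and a between-arm test can change the conclusion.

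The detectable difference of about 1.3 to 1.1 SD and the half-width of 0.94 to 0.75 SD assume two-sided 5%, equal arms, 20 to 30 evaluable subjects and no adjustment for the pre-dose score. They do not depend on what the 14 means. The 11% to 44% rates also depend on the assumed shift.

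The 14 remains unexplained, which is different from incorrect: it may be sound for the contrast it was meant for. Confidence is high that the between-arm test is missing; the documents allow no judgement on whether the trial is large enough.

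**What to change.** 1. **Section 10.** Reword the primary drug outcome as the change in comet score from Data Collection 4 to Data Collection 5, compared between acetazolamide and placebo.
2. **Section 13, analysis.** Name one primary drug analysis: regression of the post-dose comet score on arm and pre-dose score, two-sided 5%, reported with a 95% CI. Keep paired t-tests for within-subject changes with altitude.
3. **Section 13, precision.** State that with 20 to 30 evaluable subjects (10 to 15 per arm) an unadjusted t-test of change has 80% power for a between-arm difference of about 1.3 to 1.1 SD of the change, with a 95% CI half-width of about 0.94 to 0.75 SD. Add that adjustment for the pre-dose score may reduce these figures and that fewer evaluable subjects would increase them. If the earlier studies give an SD of the change, state the difference in comets too; if not, say that the SD is unknown.
4. **Section 13, the 14.** Say which contrast and unit it refers to, or do not present it as the power for the drug comparison.

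The cost is a few sentences in two sections, with no extra subjects, visits or scans. The downside is a less favourable stated figure for the drug question.

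### Section 13 names no paired test for yes/no data, so edema detection, if compared between sessions in the same subjects, would fall to Fisher's exact test and lose the pairing

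*Combined protocol and SAP*

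**What the plan says.** Section 13 (Data Analysis and Management) assigns tests by type of variable. For categorical data, "Fisher's exact test will be used to compare categorical variables". For continuous data, "Continuous variables will be analyzed with paired Student's t-test". It does not say which categorical variables or which comparisons the first rule serves, and it names no paired method for yes/no data.

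Section 10 (Study Endpoints) gives the primary outcome as "Pulmonary edema detected in lung ultrasound exams before and after taking acetazolamide". The secondary outcome is exam completion time, which is continuous.

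Section 11 (Procedures Involved) sets repeated scans of the same people: "At each of the time points noted in #9, lung ultrasound exams will be done at bedside". The itinerary in section 9 lists six data collections, the fourth and fifth at Everest Base Camp around the dose. Section 11 measures edema as a total comet count, and "a comet score will be measured again 12 hours after acetazolamide or placebo is given". It also creates two independent groups: "subjects will be randomized to receive either of the study medications medication: 250mg of acetazolamide or a placebo pill".

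Section 13 expects 20 to 30 subjects and states a minimum of 14 for 80% power on lung comets.

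**The concern.** Fisher's exact test assumes that the two proportions come from different people. Detection before versus after the dose, or at one altitude versus another, is measured on the same people. Entered into Fisher's test, each subject appears twice, and only the two totals are used. Who converted and who reverted is lost.

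When a person's scans are positively correlated, this overstates the variance of the difference. The actual false-positive rate falls well below 5%, and a true change is more likely to be reported as non-significant. The altitude comparison is the most exposed. Data Collections 1 to 4 come before or at dosing, so no treatment contrast exists yet, and a comparison between those sessions is within-subject by nature and uses all 20 to 30 people. Section 4 makes early ultrasound signs of HAPE part of the study's goal, so such a comparison is likely to be wanted.

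**Working it through.** **The plan's own figure.** The minimum of 14 for 80% power cannot be reproduced, because no effect size, SD, rate or correlation is given. At two-sided 0.05, 14 pairs imply a mean paired difference of 0.81 SD of the differences. That concerns the comet count and says nothing about a yes/no endpoint.

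**Inputs.** From section 13: N = 20 to 30 and alpha 0.05 (two-sided assumed). Assumed, because the documents are silent: detection rates p1 = 0.50 and p2 = 0.80, and within-subject correlation rho.

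**Joint probabilities.** P(positive at both) = p1·p2 + rho·√[p1(1−p1)p2(1−p2)] = 0.40 + 0.20·rho.
- At rho 0.3: both positive 0.46; convert to positive 0.80 − 0.46 = 0.34; revert 0.50 − 0.46 = 0.04; neither 0.16.
- P(both) cannot exceed 0.50, so rho cannot exceed 0.5. At that limit the probability of reverting is exactly zero.

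**Why the pairing matters.** Treated as independent, the variance of the difference is (0.25 + 0.16)/N = 0.41/N. At rho 0.3 it is (0.41 − 2 × 0.3 × 0.20)/N = 0.29/N.

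**Power.** All tables of paired outcomes were enumerated, and the probability of p < 0.05 was summed for each test:

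| N | rho | Fisher | Exact McNemar | Mid-p McNemar |
|---|---|---|---|---|
| 20 | 0 | 41% | 37% | 47% |
| 20 | 0.3 | 38% | 48% | 61% |
| 30 | 0.3 | 61% | 75% | 83% |
| 20 | 0.5 (upper bound) | 36% | 58% | 76% |
| 30 | 0.5 (upper bound) | 63% | 92% | 97% |

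**Other assumed rates, N = 20.** For 70% falling to 40%, Fisher versus exact McNemar: 35.8% v 29.2% at rho −0.2; 34.7% v 34.0% at rho 0; 33.2% v 40.7% at rho 0.2; 30.7% v 50.0% at rho 0.4. For rare findings, 5% versus 25% at rho 0.2: Fisher 27%, exact McNemar 20%, mid-p 35%.

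**Within one arm** (70% to 40%, rho 0.4), Fisher versus exact McNemar: n = 10, 7.2% v 6.2%; n = 15, 16.7% v 27.5%.

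**False-positive rate of Fisher's test** at N = 20 with 50% detection at both sessions: 2.0% at rho 0, 1.0% at rho 0.2, 0.2% at rho 0.5. Exact McNemar gives 2.3%, 1.9% and 0.9%.

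**Worked example.** Of 20 subjects, 10 are positive at the lower altitude and 16 at the higher. Fisher gives p = 0.096 however individuals moved.
- Six convert, none revert: exact McNemar p = 2 × (1/2)^6 = 0.031; mid-p = 0.031 − (1/2)^6 = 0.016.
- Eight convert, two revert: exact p = 2 × (1 + 10 + 45)/1024 = 0.109; mid-p = 0.109 − 45/1024 = 0.065.

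The paired test separates these two cases and Fisher's test cannot.

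**The case against.** A reader might infer that the plan applies Fisher's test to its primary outcome and so throws the pairing away. The documents do not go that far. Section 11 measures edema as a numeric comet score and expects a fall in that score, and the sample size in section 13 is for lung comets. A numeric score goes to the paired t-test, which keeps the pairing. No cut-off for edema present or absent is defined, and no categorical altitude comparison is specified. The yes/no reading rests mainly on the word 'detected' in section 10.

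Nor is the primary outcome the only thing that could be categorical. Side effects (section 14), evacuation or withdrawal (sections 14 and 15) and demographics (section 16) can be too. For such variables compared between two arms of 10 to 15, Fisher's test is a sound choice, so the sentence has a valid use.

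The loss of power is not universal either. It is about nil at rho 0. Exact McNemar does worse than Fisher at negative rho, with rare findings, or with few discordant pairs: it needs at least six, all in one direction, to reach p < 0.05 (five give 2 × (1/2)^5 = 0.0625).

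Finally, McNemar within an arm does not compare acetazolamide with placebo. All of this stands and limits the reach of the point. What remains is that section 13 as written offers only an unpaired test to anyone who analyses detection as yes/no across sessions.

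**Conclusion.** The point holds conditionally. If detection is analysed as yes/no between sessions, the only test that section 13 provides ignores the pairing. At 50% versus 80% and rho 0.3, the shortfall against mid-p McNemar is 61 − 38 = 23 percentage points with 20 subjects and 83 − 61 = 22 with 30. Against exact McNemar it is 10 and 14 points. At rho 0 with 20 subjects, mid-p gains 6 points and exact McNemar loses 4.

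These sizes rest on assumed rates, positive within-subject correlation and a two-sided test. Positive correlation is plausible for repeat scans of one person, but the documents do not give it. The rho 0.5 rows are the most favourable case possible for McNemar at these rates and should be read only as an upper bound. The documents do not support a claim that the primary analysis is invalid.

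**What to change.** Replace the Fisher sentence in section 13 with text to this effect:

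*Categorical variables recorded once per subject, or compared between the acetazolamide and placebo arms at a single session, will be compared with Fisher's exact test. Yes/no edema compared between two sessions in the same subjects will be compared with McNemar's mid-p test, reporting the numbers who convert in each direction. The comparison of Data Collection 4 with 5 within an arm is descriptive.*

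The wording takes effect only if a yes/no definition of edema is also stated. If several altitude pairs are to be tested, say in advance which one is the main comparison.

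The cost is two or three sentences, with no new data, subjects or staff. The downside is that mid-p does not strictly guarantee a 5% error rate, although it stayed below 5% in every null case computed (for example 3.7% at N = 30, 50% detection, rho 0.5). Exact McNemar gives the guarantee, but can have less power than Fisher when discordant pairs are few. The change does not supply a test of acetazolamide against placebo; that needs a between-arm analysis of change.

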**9. STUDY TIMELINES\***

**H00014860 Acetazolamide on High-Altitude Pulmonary Edema**  
**Version 2 – 02/10/2018**  
**INVESTIGATOR STUDY PLAN**

We will recruit subjects from the 2018 Wilderness Medical Society (WMS) Everest Base Camp Trek. The WMS 2018 Everest Base Camp Trek is a trekking trip from Lukla, Nepal (2840m) to Everest Base Camp (5400m) in Spring 2018. The duration of the trek is approximately 3 weeks. The duration of enrollment will be approximately 1-2 days during preparation part of the trip in Kathmandu, Nepal at the beginning of the trek. The estimated date for completion of primary analyses will be December 2018.

WMS Everest Base Camp Trek Itinerary

March 25	Arrival in Kathmandu, transfer to hotel (1310m)
March 26	Sightseeing in Kathmandu and preparation day **Enrollment day**
March 27	Fly to Lukla (2840m), trek to Phakding (2610m)
March 28	Trek to Namche (3440m) **Data Collection 1**
March 29	Namche and slow walk to Kunde Hospital/Kumjung
March 30	Extra day in Namche and visit Namche Bazar (3440m)
March 31	Trek to Tengboche (3860m)
April 1	Trek to Pheriche (4270m) **Data Collection 2**
April 2	Pheriche / hike Nakarsang Hill (5200m)
April 3	Pheriche
April 4	Lobuche (4910m) **Data Collection 3**
April 5	Gorakshep (5140m)
April 6	Hike to Kalapathar (5550m) / Everest Base Camp (5364m)
April 7	Everest Base Camp (5364m) **Data Collection 4 & 5**
April 8	Pheriche
April 9	Khumjung (3760m)
April 10	Manjo (2835m)
April 11	Lukla(2840m)
April 12	Fly back to Kathmandu
April 13	Kathmandu farewell dinner **Data Collection 6**
April 14	Final departure to home

\* May change slightly depending on weather, conditions, etc.

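### The plan randomises to acetazolamide or placebo but specifies no comparison of the comet score between the two arms

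*Combined protocol and SAP*

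**What the plan says.** - **Objective (section 4).** One of the two stated aims is to judge how effective acetazolamide is at reducing pulmonary edema.
- **Design (section 11).** "subjects will be randomized to receive either of the study medications medication: 250mg of acetazolamide or a placebo pill". Allocation is equal, with the "top half of the list being assigned Acetazolamide and the bottom half placebo pill".
- **Measurement (sections 9 and 11).** The dose is given at Data Collection 4, and "a comet score will be measured again 12 hours after acetazolamide or placebo is given". The itinerary lists "Data Collection 4 & 5" together at Everest Base Camp. The comet score is a total count of ultrasound lung comets.
- **Primary outcome (section 10).** "Pulmonary edema detected in lung ultrasound exams before and after taking acetazolamide". Placebo is not mentioned.
- **Analysis (section 13).** "Continuous variables will be analyzed with paired Student's t-test". Fisher's exact test is assigned to categorical variables, none of which is named. Linear regression relates comets to vital signs, with no treatment term.
- **Sample size (section 13).** "a minimum of 14 subjects will be needed to provide 80% power", with 20 to 30 subjects expected in total.

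**The concern.** The design is a two-arm placebo-controlled trial, but the analysis written for its continuous outcome is a one-sample analysis of change. Subjects in different arms are not paired and no matching is described, so the stated test cannot estimate acetazolamide minus placebo.

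What a paired test in the acetazolamide arm estimates is the drug effect plus whatever would have happened over those 12 hours anyway. A fall shared by both arms would be credited to the drug; a shared rise would hide a real benefit. Section 11 notes that "Previous studies have shown that comet scores increase with altitude", but both scans are taken at Base Camp, so that remark settles neither the direction nor the size of a shared change. Removing such a change is the purpose of the placebo arm. Leaving the comparison open also allows the test, the cut-off and the form of the endpoint to be chosen after the data are seen.

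**Working it through.** **1. Does any stated analysis compare the arms on the comet score?**

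| Analysis in section 13 | Applied to | Compares arms on the comet score? |
|---|---|---|
| Paired t-test | Continuous variables, hence the comet score | No: within subject only |
| Fisher's exact test | Categorical variables, unnamed | Not specified: no variable, cut-off, time point or groups |
| Linear regression | Comets against vital signs | No: no treatment term |

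The attached grant proposal is cited for background (section 5) and scanning methods (section 11), not for analysis.

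**2. What each contrast estimates.** Let δ be the mean 12-hour change shared by both arms and τ the drug effect. The mean change is δ + τ on acetazolamide and δ on placebo. The paired test in the acetazolamide arm tests δ + τ = 0. The between-arm contrast is (δ + τ) − δ = τ.

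**3. Size of the problem (illustration; δ is assumed).** Inputs: 20–30 subjects (section 13) split in half (section 11) gives 10–15 per arm, assuming all give both scans; two-sided 5% level (section 13 gives 0.05 but not the sidedness); τ = 0; a shared fall of d SDs of change. The paired statistic follows a noncentral t with n − 1 degrees of freedom and noncentrality d√n. For n = 10 and d = 0.5, the noncentrality is 0.5 × √10 = 1.58, the critical value is 2.262, and the probability of a significant fall is 0.293.

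| Shared fall d (SD of change) | 10 per arm | 15 per arm |
|---|---|---|
| 0 | 2.5% | 2.5% |
| 0.1 | 5% | 6% |
| 0.25 | 11% | 15% |
| 0.5 | 29% | 44% |
| 0.7 | 51% | 71% |

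If the paired test is run separately in both arms, the misleading pattern is a significant fall on drug and none on placebo. With p from the table, its probability is p(1 − p). At d = 0.5 this is 0.293 × 0.707 = 21% (10 per arm) and 0.438 × 0.562 = 25% (15 per arm). At d = 0.7 it is 0.506 × 0.494 = 25% and 0.713 × 0.287 = 20%.

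In simulation (200,000 trials; drift 0.25 and 0.7 SD; pre/post correlation 0.5 and 0.7), the two-sample test of change and ANCOVA both had two-sided type I error of 0.049–0.051. By symmetry, about half of that, 2.5%, is in the direction of a fall, which is the figure to set against the table.

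**4. The 14-subject figure.** It cannot be reproduced, because section 13 gives no effect, SD or test and does not say whether 14 is a total or per arm. Solving for the effect that gives 80% power, and then taking that effect as the between-arm difference:

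| Reading of 14 | Implied effect (SD) | Two-sample power, 10 per arm | 15 per arm |
|---|---|---|---|
| Paired sample of 14 | 0.81 | 40% | 57% |
| 14 per arm | 1.10 | 64% | 83% |
| 7 per arm | 1.63 | 93% | 99% |

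**5. Precision of the between-arm contrast.** The 95% CI half-width for the difference in change is t × √(2/n) SD: 2.101 × √(2/10) = 0.94 at 10 per arm and 2.048 × √(2/15) = 0.75 at 15 per arm.

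**The case against.** The strongest reply is that randomisation and a placebo imply a between-arm comparison, and that Fisher's exact test supplies it. Section 10 speaks of edema being detected, which can be read as yes or no, and the randomised arms are the only independent groups the documents define. A threshold might also appear in the grant proposal, which is not among the documents. This has some force, but it gives at most an under-described comparison of a binary outcome. It does not supply a between-arm test of the comet score, which section 11 sets out to measure before and after dosing.

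Three further points stand in part:

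- Section 13 does not confine the paired test to the acetazolamide arm. If it is run in both arms, the 20–25% figures for the split pattern at 0.5–0.7 SD are the relevant ones, not 29–71%. They are still far too high, and two within-arm tests side by side are not a test of the difference.
- The paired t-test is not wrong everywhere. It suits comparisons across altitudes in the same subjects, which serve the aim of detecting preclinical signs. The fault is that nothing else is provided for the treatment question.
- Every drift value is assumed, so the percentages show a mechanism and are not evidence about this trial.

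**Conclusion.** The concern holds, and it must be fixed because it affects the trial's only treatment question. No section specifies an acetazolamide-versus-placebo comparison of the comet score, and the one test assigned to that score cannot make it. This conclusion rests on the text and does not depend on any drift value.

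The size of the resulting error does depend on the shared 12-hour change, whose magnitude and direction the documents do not give. Over assumed falls of 0.1 to 0.7 SD of change, the chance of a spurious significant fall in the acetazolamide arm is 5–51% at 10 per arm and 6–71% at 15 per arm. A between-arm test is not affected by a shared change. The power calculations do not show that the trial is underpowered: the answer ranges from 40% to 99% according to what the 14 subjects meant.

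**What to change.** - **Section 10.** Define the primary endpoint as the acetazolamide-minus-placebo difference in the comet score at Data Collection 5, 12 hours after dosing.
- **Section 13, primary analysis.** Compare the arms by ANCOVA adjusted for the Data Collection 4 score, and report the difference with a 95% CI. A two-sample test of change is also acceptable. A rank-based or permutation check may be added, since comet counts may be skewed and the arms are small.
- **Section 13, other analyses.** Keep paired tests for within-subject comparisons across altitudes. If edema is also analysed as present or absent, state the cut-off and compare the arms at Data Collection 5 with Fisher's exact test.
- **Section 13, sample size.** State the test, effect and SD behind the 14-subject figure and whether it is a total or per arm, then restate power for the between-arm contrast.

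The cost is a few sentences, with no added scans or visits. The restated power may fall below 80%. If so, present the contrast as an estimate with its CI, expecting a half-width of about 0.75 to 0.94 SD of change for an analysis of change at 15 to 10 per arm.

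### The paired t-test has no arm term and uses no pre-dose scan as a covariate; regress the Data Collection 5 comet score on arm, adjusted for Data Collection 4, with a summary of Data Collections 1-3 as an optional extra

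*Combined protocol and SAP*

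**What the plan says.** Section 11 schedules the scans: "At each of the time points noted in #9, lung ultrasound exams will be done at bedside". The itinerary in section 9 places them as follows:

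- 28 March: "Trek to Namche (3440m) Data Collection 1"
- 1 April: "Trek to Pheriche (4270m) Data Collection 2"
- 4 April: "Lobuche (4910m) Data Collection 3"
- 7 April: "Everest Base Camp (5364m) Data Collection 4 & 5"

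The single dose of acetazolamide or placebo is given at Data Collection 4, and "a comet score will be measured again 12 hours after acetazolamide or placebo is given". Data Collections 1-4 are therefore pre-dose in both arms, and Data Collection 5 is the post-dose scan.

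Section 10 defines the primary outcome as oedema on ultrasound before and after acetazolamide, without naming the scans. For continuous outcomes section 13 says "Continuous variables will be analyzed with paired Student's t-test". The only regression it mentions relates comets to vital signs. It names no covariate for the drug comparison. It expects 20-30 subjects and gives 14 as the minimum for 80% power.

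**The concern.** A paired t-test compares two readings on the same people. It can say whether scores moved between two scans, but not whether they moved more on acetazolamide than on placebo. The randomised comparison is therefore missing from the stated primary analysis.

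The same sentence leaves information unused. A subject's pre-dose scores may predict the post-dose score, and the drug cannot have affected them, so they are legitimate covariates in a between-arm model. Trip size limits the sample to 20-30 and allocation is unstratified, so the arms may differ by chance in how prone subjects are to comets. Covariate adjustment is one of the few ways left to gain precision without enrolling more people.

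**Working it through.** **The plan's own figure.** N=14 for 80% power cannot be reproduced, because section 13 gives no effect size, SD, correlation or sidedness. Working back with the noncentral t at two-sided 0.05, it implies a standardised change of 0.81 if all 14 form one paired sample, or a standardised between-arm difference of 1.63 with 7 per arm. Nothing in the documents chooses between them.

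**Inputs.** From the documents: N=20-30, intended 1:1 allocation, four pre-dose scans and one post-dose scan. Assumed: equal correlation r between any two scans, equal variances, two-sided 5%.

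**Variance per subject, in units of one scan's variance.**

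- Between-arm change from Data Collection 4: 2(1−r)
- Regression adjusted for Data Collection 4: 1−r²
- Regression using all four pre-dose scans: 1−4r²/(1+3r)

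Under equal correlation the best predictor weights the four scans equally. A model with Data Collection 4 plus the mean of Data Collections 1-3 contains that predictor, so two covariates reach the third variance.

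| r | Change | DC4 | DC4 + summary |
|---|---|---|---|
| 0.3 | 1.40 | 0.91 | 0.811 |
| 0.5 | 1.00 | 0.75 | 0.600 |
| 0.7 | 0.60 | 0.51 | 0.368 |

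**Cost of estimating q covariates.** The variance is multiplied by 1+q/(N−q−3).

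- N=20: 1+1/16 = 1.0625 for one covariate; 1+2/15 = 1.133 for two.
- N=30: 1+1/26 = 1.038 for one; 1+2/25 = 1.08 for two.

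**Two covariates against a change score.**

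- N=20: 1.40/(0.811×1.133) = 1.52; 1.00/(0.600×1.133) = 1.47; 0.60/(0.368×1.133) = 1.44. Worth 44-52% more subjects.
- N=30: the same ratios with 1.08 are 1.60, 1.54 and 1.51. Worth 51-60% more.

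**Two covariates against Data Collection 4 alone.**

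- N=20: (0.91×1.0625)/(0.811×1.133) = 1.05; at r=0.5, 1.17; at r=0.7, 1.30. Worth 5-30% more.
- N=30: 1.08, 1.20 and 1.33. Worth 8-33% more.

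**Simulated power (change / DC4 / DC4 + summary).**

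| Assumed correlation | Effect | N=20 | N=30 |
|---|---|---|---|
| Equal, r=0.5 | 0.8 SD | 39/47/54% | 56/67/75% |
| First-order autoregressive, r=0.5 | 0.8 SD | 41/48/46% | 56/67/65% |
| DC4-DC5 0.9, others 0.5 | 0.5 SD | 66/65/63% | 85/85/85% |
| First-order autoregressive, r=0.9 | 0.5 SD | 65/65/61% | not used here |

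In the last row the summary costs 65−61 = 4 points at N=20; a repeat run put the two-covariate power at 62%. In the first row, adjusting for Data Collection 4 alone supplies 47−39 = 8 of the 15 points gained at N=20, and 67−56 = 11 of the 19 at N=30.

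**The case against.** The strongest reply is that equal correlation suits this schedule poorly. Data Collections 1-3 were taken 3 to 10 days earlier and about 450 to 1,900 m lower (5364−4910 = 454 m; 5364−3440 = 1,924 m), and section 11 says "Previous studies have shown that comet scores increase with altitude". A scan 12 hours earlier at the same site should predict Data Collection 5 better than one from Namche. This stands: in that case the extra covariate gives no gain or a small loss, and at N=20 with high autoregressive correlation the two-covariate model does slightly worse than a change score.

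A second reply is that the change-score column is itself a between-arm test that the plan does not contain. That also stands. The figures compare possible replacements with each other, not the plan with its replacement. The missing arm comparison is the larger fault.

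A reader might go further and infer that the plan subtracts one noisy baseline, throws three scans away, and would certainly gain precision by using all four. The documents do not support this. They give no repeatability, SD or correlation for the comet score. They never name the scans that form the pair; Data Collection 4 versus 5 is only the natural reading. The ascent scans also serve the other objective in section 4, detecting preclinical signs of HAPE.

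**Conclusion.** The point holds in two parts of unequal weight. The firm part is that the paired t-test supplies no randomised comparison and no baseline adjustment, and that regressing Data Collection 5 on arm and Data Collection 4 supplies both from data already scheduled. This rests on the text alone.

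The conditional part is the further gain from Data Collections 1-3. It is substantial if a stable subject effect dominates, and nil or slightly negative if Data Collection 4 already carries the information. The documents do not quantify that effect, so the summary covariate is optional. The percentages hold only for equal correlation of 0.3-0.7 and complete scans. They include the variance cost of the covariates but not the slightly larger t quantile.

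**What to change.** In section 13, name the primary analysis as one linear regression of the Data Collection 5 comet score on randomised arm, adjusted for the Data Collection 4 score. Report the adjusted arm difference with its 95% CI.

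Optionally prespecify one further covariate summarising Data Collections 1-3. Centre each score on its session mean, taken over both arms, before averaging a subject's available scores. Without centring, someone who missed the Namche scan would get a higher average merely because the remaining scans were at higher altitude. Decide on this covariate before unblinding.

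Do not enter the four scans as separate covariates. At N=20, with a 1 SD effect and first-order autoregressive correlation of 0.7, that gives 72% power against 78% for a change score. Do not average Data Collections 1-4 into a baseline for a within-subject change either, because that would mix the altitude trend into the change.

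The cost is SAP wording and one regression. The optional covariate uses one more degree of freedom, with a loss of up to about 4 points of power at N=20 in the unfavourable cases examined.
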